#### TRIAL SUMMARY

Trial Title:	Clinical Evaluation of an Antimicrobial Impregnated Catheter Against Peritonitis		
Local Study Reference:	(The CAP Study) UHDB/2021/021		
Trial Design:	Non Randomised Feasibility study		
Trial Participants:	Adults requiring peritoneal dialysi catheter insertion	s who require a peritoneal dialysis	
Planner Number of Sites:	1		
Planned Sample Size:	40		
Treatment Duration:	6 months		
Follow Up Duration:	6 months as per protocol then rou	utine care	
Planned Start Date:	1 st March 2024		
Planned Recruitment End Date:	30 th September 2025		
Planned Study End Date:	31 st March 2026		
	Objectives	Outcome Measures	
Primary:	To test the safety and tolerability of an antimicrobial impregnated catheter in 40 PD patients.	Adverse events	
Secondary:	To assess patient acceptability. To record peritoneal dialysis related infections and compare the incidence with locally and nationally reported rates. To assess the impact of the antimicrobial impregnation on bacterial colonisation To assess the impert of the antimicrobial impregnation on bacterial colonisation Technique failure (transfer to HD) Microorganism colonisation Antibiotic resistance pro organisms causing cathete infections		
Investigational Device:	The novel antimicrobial catheter will be manufactured by impregnating commercially available PD catheters with the antimicrobials rifampicin, sparfloxacin, and triclosan.		

Eligibility Criteria:	
	Inclusion Criteria
	Aged 18 years or older
	End stage kidney disease (ESKD) of any cause
	Elective PD catheter insertion
	Exclusion Criteria
	Documented allergy to rifampicin, sparfloxacin (or any fluoroquinolone), triclosan, or silicone
	Pregnant, likely to become pregnant, or breastfeeding
	Emergency PD catheter insertion

#### FUNDING AND SUPPORT IN KIND

Funder(s)	Financial and Non-Financial Support Given
National Institute for Health Research (Invention for Innovation)https://www.nihr.ac.uk/about- us/contact-us/contact-us.htm	Research Grant
Kimal, [name]	Support in Kind by providing the untreated catheters

#### **ROLES & RESPONSIBILITIES**

#### Sponsor

The Sponsor, University Hospitals of Derby & Burton NHS Foundation Trust, take on overall responsibility for appropriate arrangements being in place to set up, run and report the research project. The sponsor is not providing funds for this study, but has taken on responsibility for ensuring finances are in place to support the research.

#### Funder

The study is funded by NIHR.

#### **Study Management Committees**

Study Management Group

The study management group will meet regularly to oversee the day-to-day management of the study, including all aspects of the conduct of the study. Any problems with study conduct will be raised and addressed during SMG meetings.

The SMG will comprise of chief investigator and all members co investigators; at least 3 members should be present to hold a valid meeting of the SMG. The SMG will meet at least every 3 months.

#### LIST OF ABBREVIATIONS

AE	Adverse Event
APDC	antimicrobial PD catheter
CI	Chief Investigator
CIP	Clinical Investigation Plan
CKD	Chronic Kidney Disease
CRF	Case Report Form
DMEC	Data Monitoring and Ethics Committee
ESRD	End Stage Renal Disease
GCP	Good Clinical Practice
GMP	Good Manufacturing Practice
HD	Haemodialysis
IB	Investigator Brochure
ICF	Informed Consent Form
ICH	International Conference on Harmonisation of technical requirements for
	registration of pharmaceuticals for human use.
IR	Interventional Radiology
ISF	Investigator Site File
ISRCTN	International Standard Randomised Controlled Trials
NHS R&D	National Health Service Research & Development
PD	Peritoneal Dialysis
PI	Principal Investigator
PIC	Participant Identification Centre
PIS	Participant Information Sheet
QA	Quality Assurance
QC	Quality Control
QOL	Quality of Life
RCT	Randomised Control Trial
REC	Research Ethics Committee
RRT	Renal Replacement Therapy
SAE	Serious Adverse Event
SDV	Source Data Verification
SOP	Standard Operating Procedure
SMG	Study Management Group
TSC	Trial Steering Committee
TSC TMF	Trial Steering Committee Trial Master File

#### **STUDY FLOW CHART**

[figure not shown]

Figure 1 Flow diagram of routine study visits, Items highlighted in red are additional to routine care.

[figure not shown]

Figure 2 Flow diagram of additional study procedures for PD peritonitis Items highlighted in Red are additional to routine care

[figure not shown]

Figure 3 Flow diagram for additional study procedures for exit site infections, Items highlighted in **Red** are additional to routine care

[figure not shown]

Figure 4 Flow diagram for additional study procedures if PD catheter to be removed as no longer required, Items highlighted in **Red** are additional to routine care

#### **CLINICAL INVESTIGATION PLAN**

#### BACKGROUND

Chronic Kidney Disease (CKD) affects approximately 10% of the adult population. In a minority of people, CKD progresses to end-stage kidney disease (ESKD) that requires treatment with renal replacement therapy (RRT). At the end of 2017 just under 65,000 patients in the UK were receiving RRT: 55.2% had a renal transplant, 39.3% were receiving haemodialysis (HD) and 5.4% were undertaking peritoneal dialysis (PD) (1). Peritoneal dialysis (PD) is a type of dialysis used to treat people with kidney failure. To perform PD, a silicone tube is placed with one end in the abdominal cavity and the other end exiting through the skin. Fluid is run into the abdomen via the tube and then drained out again after 1-4 hours. While in the abdomen, toxins and other waste chemicals move from the body into the fluid and are then removed when it is drained out. In this way, PD partially replaces kidney function. The choice of RRT is dependent on many factors including individual preference. Recently there has been a growing appreciation of the advantages offered by forms of dialysis that can be performed in patients' own homes (home HD and PD) and the National Institute for Health and Care Excellence (NICE) recommends that all patients should be offered the opportunity to receive home dialysis (2). Home HD and PD offer the advantage of people being in control of their own therapy but are currently under-utilised. The COVID pandemic has highlighted an additional advantage of home therapies because patients who have dialysis at home are able to shield to reduce their risk of infection. Consequently, recent NICE guidelines recommended increased use of home dialysis during the pandemic (3).

The number of people performing PD in the UK is still small, with approximately 3500 prevalent PD patients and about 1700 incident patients annually (1). One of the biggest problems limiting PD use is PD catheter-related infection, classified by the site affected (exit site, catheter tunnel or peritonitis). Peritonitis can be severe, requiring hospital admission and urgent removal of the infected catheter. Infections are the major cause of hospital admissions, morbidity and mortality in PD patients and are the most common cause of PD catheter access failure within the first year (1). In 2016-17 the rate of PD related peritonitis averaged 40-50 episodes per 100 patient years across units in England and infections accounted for 20.3% of all deaths in people performing PD (1).

PD catheter infections are caused mainly by Staphylococcus aureus (including methicillin-resistant S. aureus), Staphylococcus epidermidis and Escherichia coli. A number of different approaches have been tried to reduce PD catheter infections with varying degrees of success (4). No anti-infective PD devices currently exist on the market. University of Nottingham (UoN) has developed and patented a method of impregnating, not coating, medical devices with antimicrobials to give extended protection from microbial colonisation (5). Pre-clinical studies show that PD catheters can be impregnated with the antimicrobials rifampicin, triclosan, and sparfloxacin to give long-term protection against the main causative agents of PD-associated infections. Bacteria accessing the catheter are killed and biofilm development is prevented (6).

#### 1. RATIONALE

This proposal seeks to address the clinically important and costly problem of infections associated with PD through the use of an antimicrobial-impregnated catheter, whose baseline technology has already been demonstrated to be safe and cost-effective in other clinical applications.

RRT is expensive and consumes over half of the £1.45 billion NHS England budget for CKD (2009-2010 data) (7). The approximate cost for treatment of PD-associated peritonitis is £3,103 per episode (8). In addition, peritonitis causes acute distress to patients and its management may require hospital admission and removal of the PD catheter. Recurrent peritonitis contributes to loss of peritoneal membrane function and reduced dialysis adequacy. Catheter related infections are therefore an important contributor to patients having to transfer from PD to HD. Furthermore, serial courses of antibiotics are associated with development of antibiotic resistance and other adverse events such as Clostridium difficile disease (9). Any reduction in PD infection would therefore likely improve patient experience and quality of life as well as reducing hospital admissions, technique failure, antibiotic use, antibiotic resistance and cost.

Additionally, there is a gap in anti-infective technology available to PD catheter users. Strategies for preventing PD catheter infections and peritonitis include rigorous training in the use of aseptic technique when connecting the catheter to PD fluid bags, daily application of mupirocin or gentamicin cream at the exit site and prophylactic antibiotics immediately prior to PD catheter placement. However, guidelines note that use of prophylactic antibiotics increases risk of resistance and colonisation by more unusual organisms (10).

## 1.1. Assessment and Management of Risk

The antimicrobial PD catheter and its technology have been previously developed and validated (6,11,12). Clinical and pre-clinical studies of other medical devices using the antimicrobial impregnation technology support its effectiveness. Neurosurgical shunt devices impregnated with rifampicin and clindamycin are currently sold world-wide (67 countries) as Codman® Bactiseal® (Integra Life Sciences). In a randomised controlled trial of antimicrobial-impregnated shunts and silver-treated shunts versus standard shunts in 1605 adult and paediatric patients, shunt infection rates were 60% lower for patients receiving the antimicrobial-impregnated shunt compared to standard shunt (hazard ratio 0.38, 97.5% CI 0.18 to 0.80; P=0.004) but infections were not lower with silver-treated shunts (hazard ratio 0.99, 97.5% CI 0.56 to 1.74, p=0.96). The study concluded that antimicrobial-impregnated shunts should be adopted for all patients undergoing their first ventriculo-peritoneal shunt insertion (13).

The formulation of the antimicrobial-impregnated PD catheters is the same as the antimicrobialimpregnated urinary catheters that we have tested for patient acceptability and tolerability in longterm catheter users. Results from a study of the antimicrobial urinary catheter suggest that the formulation is biocompatible following human exposure for up to 84 days (14). The antimicrobial PD catheter is also likely to be biocompatible within the delicate peritoneum. Silicone material impregnated with rifampicin, triclosan, and trimethoprim using the same technology, and implanted into the peritoneum of male rats did not show any difference in the peritoneal membrane at 7 or 31 days after implantation compared to controls. There was no evidence of peritonitis or local inflammation macroscopically or histologically (6). One of the advantages of the antimicrobial-impregnation technology over coated devices is that the antimicrobials are embedded throughout the silicone, rather than on the surface. The formulation is such that the antimicrobial molecules migrate freely within the silicone matrix, and are able to move to the catheter surface to replenish antimicrobials rinsed away to maintain a constant and high-level of antimicrobial activity at the surface, the site of microorganism colonisation (11). Both inner and outer surfaces are protected. A second advantage is that antimicrobials are released locally so that, based on known drug release profiles, they are very unlikely to cause antibiotic-associated side effects, interact with concomitant medicines, or contribute to the development of antibiotic resistance at distant sites. The antimicrobial PD catheter contains three antimicrobials from different drug classes, optimising its design according to the Dual Drug Principle. This states that the use of two antibiotics from different classes prevents emergence of resistance, as the likelihood of bacteria developing two simultaneous mutations is low (15). We have previously shown in laboratory studies that this approach prevents the generation of resistance over long periods. Specifically, catheter segments impregnated with these three antimicrobials were serially passaged daily on a bacterial lawn for 280 days and no resistance was observed. There was carryover of bacteria on the impregnated segments from one plate to the next so that the same bacterial population was exposed repeatedly to the antimicrobials (11). These three antimicrobials were selected so that at least two antimicrobials would be active against the majority of PD infection causative organisms. The third advantage of the antimicrobial-impregnated PD catheter is its long duration of protective activity. In studies that involve the flow of fluid through catheters causing elution of the antimicrobials, the antimicrobial PD catheters were able to prevent bacterial colonisation for 84 days by clinically relevant microorganisms, including those that are multi-drug resistant (6,12).

## 2. OBJECTIVES AND OUTCOME MEASURES/ ENDPOINTS

Is a PD catheter impregnated with the antimicrobials rifampicin, sparfloxacin, and triclosan well-tolerated by patients and do these data support future studies of efficacy and commercial adoption?

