## 2.1. Primary Objectives

For this feasibility study we will assess the safety and tolerability of the antimicrobial PD catheter, defined as the rate of adverse events attributable to the antimicrobials or the impregnation process encountered by PD patients.

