## 2.3. Primary Endpoint/ Outcome

The rate of adverse events attributable to the antimicrobials or the impregnation process encountered by PD patients.

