## Comparator

There is no comparator device in this study.

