## 10. STATISTICS AND DATA ANALYSIS

## 10.1. Sample Size Calculation

This is a feasibility study and a sample size calculation is therefore not required. The sample size is based on the number of PD catheters anticipated to be inserted during the recruitment period. Observation of 40 participants for 6 months with yield a total observation period of 240 patient months which should provide adequate data for comparison with nationally reported PD peritonitis rates and international quality standards (International Society of Peritoneal Dialysis recommends the rate should be below 0.4 episodes per patient year).

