## **10.3.1.** Summary of Demographic/Baseline Data and Flow of Patients

Descriptive statistics will be presented to summarize the distribution of baseline variables. Baseline variables will include comprehensive demographic and clinical variables. The continuous baseline variables will be reported with means and 95% confidence intervals (95% CI), if shown to be normally distributed, using a normality plot, otherwise will be reported with medians and interquartile ranges (IQR). The categorical variables will be reported with frequencies and percentages.

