## **10.3.2.** Primary Outcome Analysis

The primary outcome is adverse events. We will report the total number of each category of adverse event as well as the adverse event rate per participant observation month.

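### The primary analysis in section 10.3.2 reports all adverse events, not the attributable events that define tolerability, so it cannot answer the question set in section 2

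*Protocol*

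**What the plan says.** The opening of protocol section 2 asks whether the catheter is "well-tolerated by patients and do these data support future studies of efficacy and commercial adoption". Section 2.1 gives safety and tolerability a definite meaning: "defined as the rate of adverse events attributable to the antimicrobials or the impregnation process encountered by PD patients". Section 2.3 repeats this as the primary endpoint. Neither section states an acceptable level.

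Section 10.3.2 names the primary outcome simply as adverse events, as the Trial Summary does, and sets the analysis: "We will report the total number of each category of adverse event as well as the adverse event rate per participant observation month". It does not mention attribution, the number of participants affected or an interval.

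The study has one arm ("There is no comparator device in this study", section 7.1). Section 10.1 says "This is a feasibility study and a sample size calculation is therefore not required" and gives the expected exposure as 240 patient-months. Section 3 states a more modest purpose than section 2: to gather preliminary information for the design and feasibility of a randomised trial.

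**The concern.** The objective, the endpoint and the analysis should describe the same quantity. Here the first two concern events caused by what is new in the device, while the third covers every untoward occurrence in people with kidney failure on dialysis. Many of those events would happen with any catheter, and there is no comparator arm from which to subtract them.

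A rate per participant-month also cannot tell one participant with several events from several participants with one event each. For a question about how well patients tolerate an implant, that distinction matters.

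What is at stake is the conclusion. If section 10.3.2 is followed literally, the headline figure is dominated by background events. If the authors then extract the attributable events afterwards, a small count or a zero could be presented as supporting commercial adoption, although 40 uncontrolled participants leave a wide range of true risk open.

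**Working it through.** **1. The plan's own figure.** 40 participants × 6 months = 240 participant-months, or 240 / 12 = 20 patient-years. Section 10.1 reproduces.

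**2. Endpoint against analysis.** Sections 2.1 and 2.3 count attributable events; section 10.3.2 counts all adverse events. To see the size of the gap, take the local peritonitis rate in section 8.2, 0.37 per patient-year. Over 20 patient-years that is 0.37 × 20 = 7.4 expected episodes. Peritonitis meets the section 8.1 definition of an adverse event, so this alone adds 7.4 / 240 = 0.031 per participant-month, even if no episode has anything to do with the antimicrobials. The reported rate could be well above zero while the defined endpoint is zero.

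**3. Events against participants.** Four attributable events give 4 / 240 = 0.0167 per participant-month in either of two cases:
- all four in one participant: 1/40 = 2.5% affected (exact 95% CI 0.1% to 13.2%);
- one in each of four participants: 4/40 = 10% affected (2.8% to 23.7%).

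The stated statistic is the same in both.

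**4. What 40 participants can show.** The exact (Clopper-Pearson) upper 95% limit for x of 40 is the 0.975 quantile of Beta(x + 1, 40 − x). For x = 0 this is 1 − 0.025^(1/40) = 0.0881. The exact Poisson upper limit for the rate is half the 0.975 chi-square quantile on 2x + 2 degrees of freedom, divided by 240. For x = 0 it is 3.689 / 240 = 0.0154 per month, or × 12 = 0.18 per patient-year.

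| Affected (of 40) | Proportion | Upper 95% limit | Upper limit, events per participant-month |
|---|---|---|---|
| 0 | 0% | 8.8% | 0.0154 |
| 1 | 2.5% | 13.2% | 0.0232 |
| 2 | 5% | 16.9% | 0.0301 |
| 3 | 7.5% | 20.4% | 0.0365 |
| 4 | 10% | 23.7% | 0.0427 |

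The last column assumes one event per affected participant and full exposure. Section 6.5 withdraws participants when the catheter is removed, so 240 is a maximum. The protocol gives no loss figure. Assuming 10% to 30% lost exposure, the zero-event limit rises from 0.0154 to between 0.0171 and 0.0220 per month.

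**5. Would a pass mark be a safe remedy?** With 40 participants and a true attributable risk of 5%, the binomial probabilities are P(0) = 0.129, P(at most 1) = 0.399 and P(at most 2) = 0.677. A rule allowing at most one affected participant would therefore fail such a device about 60% of the time (1 − 0.399), and a rule allowing two about 32% (1 − 0.677). If the true risk were 10%, the rule allowing two would still pass it with probability 0.22. These rules are illustrative; the protocol contains none.

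**The case against.** The best defence is that this is a feasibility study whose working text is already estimation. Sections 2.1 and 2.3 speak of a rate, section 3 of preliminary information, and the sentence opening section 2 is an unlabelled lead-in. That stands in part, and it is why rewording is enough.

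Second, intervals and participant-level summaries are often left to a statistical analysis plan, which is not at hand. Also true: a missing interval alone would not be a finding. But section 10.3.2 does state the primary analysis, and what it states is not the endpoint of section 2.3. One might reply that reporting by category covers this, because section 8.1 separates adverse device effects from other events. That class relates to the device as a whole, including use errors and malfunctions, and the rate is not split by it.

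Third, a reader might infer that any adverse event rate at all could be declared well tolerated. The protocol does not support that. Section 6.5 allows early stopping over safety or tolerability, section 10.4 allows termination for unacceptable risk, section 8.2 requires review if peritonitis exceeds 0.37 per patient-year, and section 8.3 provides continuing risk-benefit review. Patients also score tolerability from 1 to 10 (sections 6.4 and 10.3.3). These are real safeguards and relevant data. They do not define what the primary endpoint must show at the end: stopping rests on judgement, the score has no cut-off, and the peritonitis figures (including the English range of 40 to 50 per 100 patient-years in the Background) concern a secondary outcome. The peritonitis trigger is also a weak signal. With 7.4 episodes expected at the local rate, 8 or more would occur with probability 0.46 if the catheter changed nothing.

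Fourth, a single cut-off on any attributable event would weigh a mild event like a serious one and could often reject a low-risk device, as step 5 shows. This objection stands.

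**Conclusion.** The point holds as a mismatch between question, endpoint and stated analysis. Section 10.3.2 as written produces a figure for all adverse events that cannot answer section 2, and it hides both the number of participants affected and the uncertainty. On the endpoint as defined, zero affected of 40 still allows a risk up to 8.8%, and two affected allow up to 16.9%. These limits assume that all 40 are evaluable and act independently; losses would widen them.

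Three stronger readings should be resisted. The missing sample size calculation and comparator are ordinary features of a single-arm feasibility study, not errors. The protocol does not leave safety unguarded during the study. And nothing in it makes a numerical pass mark obligatory; an honest estimate with its interval would serve the aim in section 3.

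The change is worth making before the first analysis. The data remain usable either way, but the claim about commercial adoption goes beyond what this design can show.

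**What to change.** 1. **Section 10.3.2.** Make the primary statistic the number and proportion of participants with at least one adverse event attributable to the antimicrobials or impregnation, with an exact 95% confidence interval. Keep the rate per participant-month as a companion, showing attributable and all adverse events separately. Say which causality grades count as attributable. Because section 8.3.1.2 grades the relationship to the device and procedure together, the case report form should also record whether the antimicrobials or impregnation are the suspected cause. Align the Trial Summary with this.
2. **Section 2.** Reword the opening as estimation: to estimate the proportion of participants with attributable events, with its interval, to inform a randomised trial. Remove the suggestion that these data can support commercial adoption.
3. **Optional.** If the sponsor wants a progression mark, it should set one before the first analysis, weighing severity and the operating characteristics in step 5. If the rule compares the exact upper 95% limit with the mark, a mark at or below 8.8% cannot be met with 40 participants.

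The cost is a few sentences, one form item and one standard interval; there are no extra patients or visits. The small downside is that even zero attributable events must be reported with an upper limit near 9%.
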